## **7.1 Role of Trial Nurse (TN) and Study Coordinator**

A trial nurse (TN) working closely with the PI (backed up and sharing call with a trained clinical research coordinator) will be available 24 hours a day, 7 days per week on a special pager and cell phone, and shall be the first portal of contact for study subjects. The TN will also be responsible for following up with subjects in between scheduled visits (in response of calls by the subjects or at regular scheduled phone calls every three months). H/she will help assess attributability of any new symptoms to the study intervention (section 10.5) and instructing subjects when it is necessary to seek medical attention. The TN and study coordinator shall be blinded to the study group allocation. They will be supplied with management algorithms detailing the standards of care in dealing with the most recognized side effects of the study intervention (25, 102, 103). The TN and coordinator will be able to access subjects' electronic case report form (eCRF) to track their course throughout the study and document any events. The TN and study coordinator shall be overseen by and have unfettered access to the study PI regarding any trial related clinical questions. They shall have direct access to the External Medical Safety Monitor (see below) in the absence of the PI.

## **7.2 Adverse Event Management Protocol**

Mild adverse events (Table 2, Category A) encountered by any subject regardless of assigned treatment will be recorded, relayed to the safety monitoring team and closely followed by the TN. More concerning adverse events (Category B) will be managed by withholding the study intervention for 2-4 weeks pending resolution of symptoms or biochemical abnormalities. Subjects will then be restarted on the lower dose (40 mg/day) of the study intervention (atorvastatin or placebo). Depending on the dose at which adverse events occurred, the process can be repeated, tapering the dose down to attrition as deemed appropriate by the PI in consultation with the external medical safety monitor (MSM). Intolerable or potentially serious adverse events that recur or persist in spite of dose reduction, along with other serious adverse events listed in Section 8 will lead to unblinding and determination of endpoint for that subject in the trial. A statin expert physician consultant is available at the Chicago site to advise regarding adverse event management in individual cases.

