### **3.2 Blinding**

The study is designed as a double-blind, placebo-controlled clinical trial. Enrolled subjects will be blinded to treatment rendered, as will the PIs, outcomes assessors processing the radiological biomarkers, the trial staff at the Chicago site and the Data Coordinating Center (DCC) staff at the Baltimore site. Atorvastatin and placebo capsules will be formulated by a third party pharmacy representing two different doses of atorvastatin (40 and 80mg) or placebo. The Research Pharmacy at the Chicago site shall be informed electronically about the treatment allocation (see Section 3.3 Randomization), and it shall dispense the appropriate drug or placebo in a 6-month supply, given at enrollment then mailed by the study team biannually, one month ahead of expected date of exhausting the supply. Subjects in the treatment group will receive unlabeled color coded capsules containing pulverized atorvastatin tablets in the designated doses. Subjects in the control group will receive identical looking color coded capsules containing inactive filler. In the case of dose de-escalation, the Research Pharmacy shall be instructed about the decision to lower the dose, and it shall dispense capsules of different color indicating the lower dose, or identical colored placebo capsules, without breaking the blind to the patient or research team.

The Baltimore statistician shall prepare safety reports including comparison of adverse events (AEs) and interim outcome measures by treatment group labeled as A or B without identifying either as active treatment (See Sections 9.4 on Data Monitoring and 10.3 on Quality Assurance and Data and Safety Monitoring). If a concern is raised about safety and the need to suspend trial enrollment, the independent medical safety monitor (IMSM) may request to identify A or B groups as treatment or placebo. Individual subjects will not be identifiable in the safety reports, maintaining the double-blinding if the trial is resumed.

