## **7.3 Common Adverse Events**

### **7.3.1 CA hemorrhage**

Best care criteria defined by the American Heart Association (AHA) guidelines for management of ICH will be the standards of care for all general medical care in this protocol. Specifically, the guidelines are (i) Stroke Council special writing group

guidelines for the management of ICH (74), (ii) European Stroke Initiative (EUSI) Guidelines for the management of intracranial hemorrhage (104), and (iii) the AANS guidelines for management of elevated intracranial pressure (105). Management may include blood pressure reduction, use of platelets and prothrombotic agents, and use of a surgical procedure. The care team is required to preserve life and functional outcomes in these instances. The management of each adverse event will be recorded and will be reviewed by the safety monitoring team.

If a CA symptomatic bleed is verified as per adjudicated criteria (20), including a rebleed of prior lesion or new bleed from another lesion, then a safety endpoint will have been reached, and the subject will be notified, and decision is made to cease the study intervention. Patients will remain in the study for the remaining scheduled follow-ups. The lesion that has hemorrhaged shall be considered for treatment as per current guidelines and standards of care.

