## 8. CRITERIA FOR INTERVENTION DISCONTINUATION

Atorvastatin/Placebo administration will be discontinued for any of the following reasons (designated as serious AEs or Category C in the preceding Table 2):

- Symptomatic intracerebral hemorrhage (ICH) whether primary, arising from index cavernous malformation that previously bled, or in other lesion, or other ICH of any kind
- Severe allergic reaction
- Rhabdomyolysis
- Markedly elevated liver enzymes
- Liver failure
- Pancreatitis
- Pregnancy
- Intolerable adverse events that persist or recur after serial dose reduction.
- In the investigator's judgment, withdrawal from the trial would be in the subject's best interest (Drug interaction/glycemic control).
- The subject or legal representative withdraws consent, or patient undergoes surgical resection or irradiation of CCM lesion, other brain surgery or irradiation for any cause.
- Patient develops clinical indications for statin use for cholesterol or cardiovascular indications unrelated to CCM.

If one or more of these events occur after commencing the study drug, the subject will be considered to have reached a safety endpoint. Study drug or placebo shall be discontinued. All subjects reaching safety endpoints will be followed through the 24-month follow up visit as a part of the outcome assessment for the study. An attempt will be made to contact subjects who withdraw from the study or who are lost to follow up for safety evaluation. If these subjects wish not to cooperate there will be no additional follow up.

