### **9.3.2 Potential Missing Data, Attrition and Premature Trial Endpoint**

We considered all potential causes of missing data and we developed strategies to minimize and mitigate them. In initial pilot studies, 34 of 177 (19%) QSM assessments in CA patients were unusable due to technical reasons (mostly patient movement during image acquisition). We eliminated this problem in the most recent 25 consecutive cases with specific patient instructions. We now implement a further step of reviewing the QSM acquisition, and rapidly processing it (10 minutes on local Matlab computer terminals in our laboratory). This allows us to repeat the QSM acquisition if needed, before proceeding with contrast injection for DCEQP measurements. This “chaperoned biomarker acquisition” reduces to virtually zero the rate of missing QSM measures (See letter by [name] and Protocol Section 6.5). We nevertheless project up to 10% missing biomarker data related to imaging (claustrophobia, etc.). We further project an additional 10% missing data due to imperfect follow-up, higher than that recorded in recent trials conducted by our teams (113, 114).

Up to 20% of subjects randomized to atorvastatin (10% of trial subjects) might not tolerate the 80 mg/day dose. Many will continue the drug at the lower dose. In fact, **serious side effects or intolerance of the lower dose are expected to result in attrition in less than 5% of cases**, per extensive meta-analyses of trial experience with the study drug (See Protection of Human Subjects; and Protocol section 7.3). Another **20-30% of cases might reach a prespecified study endpoint** because of SH, and they would also stop the drug before the end of the 2-years follow-up. All subjects who stop the drug, and those with non-compliance as defined, will still be followed for the full 2 years with scheduled clinical and imaging assessments, and will be included in the **primary analysis per intention-to-treat**.

To permit secondary analysis per treatment rendered, at the power and Type I error described above, we decided to **expand the sample size by an ample 37.5%, factoring the highest combined estimates of missing data and attrition.**

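### Section 7.2 makes unblinding automatic for serious adverse events listed in Section 8, symptomatic hemorrhage included, although these subjects stay in outcome assessment to month 24

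*Combined protocol and SAP*

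**What the plan says.** Section 7.2 ends its account of adverse event handling with a mandatory rule. Events that continue or come back once the dose is lowered, "along with other serious adverse events listed in Section 8 will lead to unblinding and determination of endpoint for that subject in the trial". It attaches no test of clinical need and names no recipient of the assignment.

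Section 8 describes its list of discontinuation reasons as "designated as serious AEs or Category C in the preceding Table 2". The first entry is "Symptomatic intracerebral hemorrhage (ICH) whether primary, arising from index cavernous malformation that previously bled, or in other lesion". Any listed event is a safety endpoint, and capsules are stopped in either arm.

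Follow-up does not stop. Section 8: "All subjects reaching safety endpoints will be followed through the 24-month follow up visit as a part of the outcome assessment for the study". Section 7.3.1, on hemorrhage: "Patients will remain in the study for the remaining scheduled follow-ups". Section 9.3.2 says that subjects who stop the drug "will still be followed for the full 2 years with scheduled clinical and imaging assessments" and enter the primary intention-to-treat analysis. The same section projects that "20-30% of cases might reach a prespecified study endpoint" because of symptomatic hemorrhage.

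On blinding, Section 3.2 says: "Enrolled subjects will be blinded to treatment rendered, as will the PIs". It extends this to the biomarker assessors, the Chicago trial staff and the coordinating center staff. The synopsis adds the treating team, Section 7.1 the trial nurse and coordinator, and Section 9.1 the clinical personnel. The exception in Sections 3.2 and 9.1 is at group level: A or B may be identified if a safety concern arises.

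**The concern.** Stopping capsules at a safety endpoint does not require the code, because active drug and placebo are stopped alike. Section 7.2 breaks the blind anyway, and does so for a group defined by outcome.

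That group is informative for the trial. Section 2.2 reports a mean QSM increase of 44% in previously stable lesions that grew or bled, and no clinical event in the recent-hemorrhage pilot cohort without a threshold rise in QSM.

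Several outcomes still to be collected rest on judgment or self-report: mRS at every contact, MMSE and quality of life at months 12 and 24, causality of adverse events (Section 10.4.2.1), and lesion diameter. The PI characterizes the diameter (Section 6.5.1), and it feeds the 2 mm expansion outcome in Section 9.2. If the person rating or reporting knows the arm, differences between arms in these outcomes can partly reflect expectation.

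**Working it through.** The point is mainly one of reading passages together. The arithmetic only sizes it.

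**1. Denominator.** Section 9.3.1 assumes SD 30, two annual scores with correlation 0, a difference of 20, two-sided alpha 0.05 and power 0.90.
- Effective SD = 30 × √[(1 + 0)/2] = 21.21.
- n per arm = 2 × (1.960 + 1.282)² × 21.21² / 20² ≈ 23.6, so 24 by the normal approximation and 25 by the noncentral t. The plan states 25.
- 25 / (1 − 0.375) = 40 per arm, 80 in total.

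The plan's figures reproduce. The unblinding point does not depend on them beyond the total of 80.

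**2. Size of the group.** Section 9.3.2 gives 20-30% for hemorrhage.
- 0.20 × 80 = 16.
- 0.30 × 80 = 24.
- With bleeds split equally between arms (an assumption), 8 to 12 per arm.

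**3. Assessment still to come.** A subject who bleeds before the month 12 visit still has both imaging visits ahead. One who bleeds in year 2 still has the month 24 visit and any remaining quarterly calls. Remaining time therefore runs from almost 24 months to almost none. If events were spread evenly over follow-up (an assumption), it would average 12 months.

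**4. The passages side by side for a subject with a verified bleed.**

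| Question | Section 7.2 with Section 8 | Section 7.3.1 | Synopsis, 3.2, 7.1, 9.1 |
|---|---|---|---|
| Study capsules | Stopped | Stopped | Not addressed |
| Subject's assignment | Unblinded | Silent; subject is told an endpoint was reached | Blinded, with no exception for a single subject |
| Who is told the arm | Not stated | Not stated | Nobody listed as blinded |
| Later assessment | To month 24 | Remaining scheduled visits | Assessors blinded |

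The second row cannot be followed as written. The third row leaves the consequence open.

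**5. Is the code needed to act?** Section 3.2 already lets the research pharmacy lower a dose in either arm without the subject or research team learning the assignment. The same route can stop capsules.

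**The case against.** The strongest reply is that Section 7.2 is a specific exception to a general blinding rule, and that the hemorrhage section never mentions unblinding. That silence is real and makes the handling of bleeders less clear. It does not cancel a mandatory sentence that points to a list headed by hemorrhage, and no section presents Section 7.2 as an exception.

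Three stronger readings are tempting, and the documents do not support them.

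- **Every subject reaching a Section 8 endpoint is unblinded.** Section 7.2 speaks of serious adverse events. Section 8 also lists consent withdrawal, resection or irradiation, a new statin indication and investigator judgment. Only the label over the whole list brings these in. Subjects who withdraw and do not cooperate also have no further follow-up.
- **Later outcomes are in fact assessed with the arm known, so the primary result is biased.** No recipient is named. The trial nurse and coordinator, who collect mRS by telephone, are stated to be blinded, as are the QSM readers. Images are de-identified, traceable by subject number and scan date. The bleed that triggers unblinding also precedes it. What remains is that Section 7.2 shields none of these people, and that the most exposed outcomes are secondary. Loss of QSM through a resection influenced by knowledge of the arm is an inference; the plan does not say how QSM is handled after resection.
- **Up to 28 subjects are unblinded with 24 months left.** That count adds 5% for intolerance to the upper hemorrhage figure (0.35 × 80 = 28). Section 9.3.2 says less than 5%, and 24 months applies only to an event at the very start.

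**Conclusion.** The point holds as a conflict between sections with a foreseeable effect on the conduct of the trial. Followed as written, Section 7.2 unblinds an outcome-defined group that remains under outcome assessment and in the primary analysis. The projected size is 16 to 24 of 80 subjects from hemorrhage alone. This rests on the plan's own 20-30%, which is worded as a possibility, and the follow-up affected depends on when the bleeds occur.

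Confidence is high on the wording and the conflict. It is lower on the consequence: that mRS, MMSE, quality of life, causality or lesion diameter would be judged with the arm known is possible, not shown, because the recipient is unstated. Bias in the QSM result is not established. The text should be corrected because the exposure is avoidable and the remedy is cheap.

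**What to change.** Reconcile Section 7.2 with Sections 3.2, 7.3.1 and 9.1 by removing automatic unblinding:

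- At a safety endpoint, capsules are stopped under code through the research pharmacy. The stopping rule itself is unchanged.
- An individual code break is by exception, limited to those who need the assignment for the subject's care, and logged with date and recipient. When care requires it is for the sponsor to define.
- Outcome assessors, QSM and DCEQP readers, the trial nurse and the coordinator stay blinded.
- At this single site the PI may be both treating clinician and measurer of the lesion. If the PI has to learn an assignment, that subject's later PI-made measurements are flagged, and a sensitivity analysis excludes them.
- Section 7.3.1 states the same handling for hemorrhage.

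The cost is protocol wording, a code-break log, a data flag and one sensitivity analysis. The downside is that subjects who stop learn their arm later.

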## **7.3 Common Adverse Events**

### **7.3.1 CA hemorrhage**

Best care criteria defined by the American Heart Association (AHA) guidelines for management of ICH will be the standards of care for all general medical care in this protocol. Specifically, the guidelines are (i) Stroke Council special writing group

guidelines for the management of ICH (74), (ii) European Stroke Initiative (EUSI) Guidelines for the management of intracranial hemorrhage (104), and (iii) the AANS guidelines for management of elevated intracranial pressure (105). Management may include blood pressure reduction, use of platelets and prothrombotic agents, and use of a surgical procedure. The care team is required to preserve life and functional outcomes in these instances. The management of each adverse event will be recorded and will be reviewed by the safety monitoring team.

If a CA symptomatic bleed is verified as per adjudicated criteria (20), including a rebleed of prior lesion or new bleed from another lesion, then a safety endpoint will have been reached, and the subject will be notified, and decision is made to cease the study intervention. Patients will remain in the study for the remaining scheduled follow-ups. The lesion that has hemorrhaged shall be considered for treatment as per current guidelines and standards of care.

### **7.3.2 Myositis/Rhabdomyolysis.**

Skeletal muscle inflammation is a rare but well recognized adverse event in statin therapy. The severity of this inflammation ranges from mild myalgia to multi-organ system failure secondary to myoglobinuria (Table 2). Management should follow standard of care and is to be dictated by the PI based on symptom severity/degree of lab value elevation, in consultation with the on-site statin consultant. Management may include vigorous hydration, alkalinization of urine, correcting electrolytes, and in extreme cases hemodialfiltration. The decision to declare a safety endpoint in the case of myositis, versus the decision to decrease the dose of drug will depend on severity of the myositis as per established guidelines.

### **7.3.3 Hepatotoxicity**

Drug-induced liver insult runs a spectrum from asymptomatic elevation of liver enzymes to acute fulminant hepatitis. However, it is now well recognized that statin-related hepatic adverse events are exceptionally rare and unpredictable. Analysis of safety data pooled from 49 clinical trials of atorvastatin in 14,236 patients showed that persistent elevation in hepatic transaminases does not exceed 0.6% (106). Statin-induced liver insult almost invariably occurs in cases with pre-existing chronic liver disease (e.g. viral/ alcoholic hepatitis, etc.) or concomitant ingestion of hepatotoxic drugs (25, 102, 103). All subjects in this study will be screened for risk of hepatic toxicity prior to enrollment, as per current recommendations by both the American College of Cardiology/American Heart Association (ACC/AHA) and FDA (107). The FDA has recently revised safety guidelines to remove the need for routine monitoring of liver enzymes in patients taking statins. To detect asymptomatic elevation of liver enzymes, enrolled subjects will also have their liver enzymes checked at 3 months and at each follow up visit. Additionally, subjects exhibiting any evidence of liver dysfunction at any point throughout the trial will undergo extensive hepatitis workup and further management in accordance with the trial adverse events management algorithms. (Table 2)

**7.3.4 Other adverse events.**

Other commonly reported adverse reactions (incidence  $\geq 2\%$  and greater than placebo) regardless of causality, reported in patients treated with atorvastatin in previous placebo-controlled trials, such as nasopharyngitis, diarrhea and urinary tract infection, will be individually reported and managed as elaborated in section 7.2.

**Table 2 below summarizes potential adverse events by body systems that have been reported with the study intervention and other statin medications.**

Adverse Event Category	Mild AE (Category A)	Moderate AE (Category B)	Serious AE (Category C)
General/Constitutional			
• Malaise / Fatigue	Tolerable/self-limited	Intolerable/persistent	Recurrence after dose reduction
• Pyrexia	38.0 - 39.0 degrees C (100.4 - 102.2 degrees F). self-limited	Intolerable/persistent	Recurrence after dose reduction
• Allergic reactions	Erythema multiform	Mild self-limited classic allergic responses such as pruritis, hives or urticaria, cutaneous vasodilation ("flushing"), development of edema (peripheral or airway), peripheral vasodilation (hypotension), bronchospasm, and/or tachycardia.	Recurrence after dose reduction/Anaphylactic reaction/Steven-Johnson syndrome / Toxic epidermal necrolysis
Muscular			
• Musculoskeletal pain (3.5%), muscle spasm (3.6%), arthralgia (6.9%)	Tolerable/self-limited	Intolerable/persistent	Recurrence after dose reduction
• Joint swelling	Asymptomatic; clinical or diagnostic observations only.	Intolerable/persistent	Recurrence after dose reduction
• Incipient Myositis	CK < 3 x ULN, no relevant clinical symptoms.	CK >3 x ULN Plus new elevation of ALT, irrespective of musculoskeletal symptoms.	Recurrence after dose reduction
• Definite Myositis (0.08%)		Myalgia Plus markedly elevated serum creatine kinase >10 x ULN	Recurrence after dose reduction
• Rhabdomyolysis			Myositis Plus evidence of new renal impairment +/- other organ system failure

Adverse Event Category	Mild AE (Category A)	Moderate AE (Category B)	Serious AE (Category C)
• Tendon Rupture			Tendon Rupture
GI/Hepatobiliary			
• Pharyngeal pain (2.3%) , dyspepsia (4.7%), nausea (4%), bloating, eructation, flatulence or diarrhea (6.8%)	Tolerable, self-limited	Intolerable/persistent	Recurrence after dose reduction
• Hepatitis (0.6%)	Elevated Transaminases (ALT, AST): <ULN - 3.0 x ULN, no relevant clinical symptoms.	Elevated Transaminases (ALT, AST): >ULN - 3.0 x ULN, no relevant clinical symptoms.	Recurrence after dose reduction / ALT >3.0 ULN; >3 x ULN with the appearance or worsening of fatigue, nausea, vomiting, right upper quadrant pain or tenderness, fever, rash, or eosinophilia
• Acute Liver failure			Hepatitis plus abnormal plasma levels of ammonia, bilirubin, lactic dehydrogenase, and alkaline phosphatase
• Cholestasis		Serum conjugated bilirubin >1.5 x ULN; clinical jaundice.	Recurrence after dose reduction
• Pancreatitis			Severe abdominal pain; vomiting plus enzyme elevation (amylase 200 above ULN with elevated lipase levels) or radiologic findings
Nervous System			
• Dizziness, insomnia (3%), Depression, nightmares	Tolerable, self-limited	Intolerable/persistent	Recurrence after dose reduction

Adverse Event Category	Mild AE (Category A)	Moderate AE (Category B)	Serious AE (Category C)
• Cognitive impairment	1 points drop in MMSE; not interfering with work/school/life performance; specialized educational services/devices not indicated	>1 points drop in MMSE; interfering with work/school/life performance; specialized educational services/devices not indicated	Persistence after dose reduction
• Symptomatic Intracerebral Hemorrhage			New onset neurological symptoms Plus intraparenchymal or intralosomal hemorrhage confirmed on imaging studies
Endocrine system			
• Hyperglycemia		New impaired glucose tolerance/glycemic control	Persistence after dose reduction
Respiratory			
• Nasopharyngitis (8.3%)	Tolerable, self-limited	Intolerable/recurrent	Recurrence after dose reduction
• Epistaxis	Mild episode, self-limited	Requiring medical attention, Recurrent episodes	Recurrence after dose reduction
Genitourinary			
• Urinary tract infection (5.7%)	Simple cystitis	Recurrent cystitis /pyelonephritis	Recurrence after dose reduction

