### 3.4 Method of Dosing

After randomization, enrolled subjects in both groups will be given unlabeled color-coded capsules to be taken once daily. In the absence of signs or symptoms of statin-related adverse events (Table 2), subjects will be instructed to continue on the same regimen. The dose may be de-escalated based on subject's tolerance. Subjects reporting adverse events per pre-specified criteria (Category B detailed below) will be put onto the lower dose (40 mg/day) of atorvastatin, with a different color. Subjects randomized to the placebo arm will receive an equivalent supply of identical color unlabeled capsules, devoid of the active ingredient, to be administered in the same fashion as the active drug. They will undergo the same evaluations, dose adjustments, and follow up visits as the treatment cohort.

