## 5. STUDY INTERVENTION

### 5.1 Intervention, Administration, and Duration

Study drug will be administered orally as a single daily dose in the morning. Subjects in the treatment group will be started on their corresponding dose 80mg of atorvastatin or placebo. Should the subject report an adverse event meeting pre-specified criteria (Adverse events Category B below), he/she will be put on the lower dose (40 mg) of drug or matched colored placebo capsule.

Administration of study drug shall continue once daily dose in the morning for 24 total months with scheduled visits and repeat imaging at 12 and 24 months from enrollment, unless the subject reaches attrition or a safety endpoint before then. If new symptoms arise at any point after starting the study intervention subjects will be contacted by the study-designated TN for further assessment and be provided with instructions regarding continuation of study intervention based on the study adverse events management protocol (Section 7).

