## 7. MANAGEMENT OF ADVERSE EXPERIENCES

In the event of an adverse event (Table 2), the first concern will be for the safety of the subject. Subjects will be closely monitored and are required to notify the trial PI or designated TN of any new symptoms that occur following treatment onset. Managed adverse events include all new symptoms, whether expected or unexpected, which are assessed by the TN, in consultation with the on-site statin expert physician, to be reasonably or possibly related to the study intervention. All adverse events that the study team is notified about will trigger at least an unscheduled telephone evaluation. During the evaluation, a member of the study team will assess the seriousness of the reported event, its attributability to the study intervention and advise the subject regarding the treatment plan, including whether to continue on the study drug (99, 100). Serious criteria, definitions, and guidance for reporting follow in section 10.4: Adverse Experience Reporting.

Historically, very low levels of low-density lipoproteins (LDL) have been sporadically associated with some detrimental effects. However, clinical trials on statin therapy have not demonstrated any substantial correlation between lower LDL levels and safety. There is no evidence that lowering low-density lipoprotein levels in people with normal cholesterol profile is inherently unsafe (101).

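### Category B in Table 2 includes mild airway edema, bronchospasm and hypotension, and the written default after Category B is a restart at 40 mg, with no allergy exception and no threshold separating these signs from reactions that stop drug

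*Combined protocol and SAP*

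**What the plan says.** Table 2 (Section 7.3.4) grades allergic reactions in three columns. The Category B cell opens with "Mild self-limited classic allergic responses such as pruritis, hives or urticaria" and goes on to list flushing and "development of edema (peripheral or airway), peripheral vasodilation (hypotension), bronchospasm, and/or tachycardia". The Category C cell lists recurrence after dose reduction, anaphylactic reaction, Stevens-Johnson syndrome and toxic epidermal necrolysis.

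Section 7.2 withholds drug for 2-4 weeks after a Category B event, and then: "Subjects will then be restarted on the lower dose (40 mg/day) of the study intervention (atorvastatin or placebo"). Section 3.4 says: "Subjects reporting adverse events per pre-specified criteria (Category B detailed below) will be put onto the lower dose (40 mg/day) of atorvastatin". Section 5.1 says of such a subject that "he/she will be put on the lower dose (40 mg) of drug or matched colored placebo capsule".

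Section 8 stops drug for "Severe allergic reaction", and also when the investigator judges that "withdrawal from the trial would be in the subject's best interest". Section 7 has the study team assess each reported event and "advise the subject regarding the treatment plan, including whether to continue on the study drug".

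**The concern.** Airway edema, bronchospasm and hypotension are the signs for which re-exposure to a suspected drug is most hazardous. The written pathway nevertheless treats them, when judged mild, in the same way as intolerable fatigue or dyspepsia: hold, then restart at half the dose. If nobody uses the available discretion, a subject whose airway or circulatory signs have settled is given the suspected drug again at 40 mg.

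The boundary with the drug-stopping category rests on adjectives alone. One reader may call an episode of bronchospasm mild and self-limited, and another may call it anaphylactic or severe. The first grade restarts drug and the second stops it.

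**Working it through.** The plan states no figure to reproduce, so the main check sets the governing text side by side.

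1. **Signs in Category B.** Airway edema, hypotension and bronchospasm are all named in the Category B cell (Table 2). The qualifier in that cell is mild and self-limited, although the column is headed moderate.
2. **Consequence of Category B.** Section 7.2 writes the first restart as something that will happen. The discretion it gives the PI and the safety monitor is attached to repeating the process. Sections 3.4 and 5.1 repeat the move to 40 mg, and no event type is exempted in any of the three.
3. **Stops in the same row.** Recurrence after dose reduction stops drug, but only after re-exposure. The remaining stops are three named diagnoses, and no signs, vital-sign limits or treatment needs are given for recognising an anaphylactic reaction.
4. **Section 8.** A severe allergic reaction stops drug; severe is not defined.
5. **Other possible thresholds.** The seriousness criteria in 10.4.1.2 are said to correspond generally to Categories B and C together, so they do not separate the two. Grades 4 and 5 trigger SAE reporting, not a drug stop. Other rows of Table 2 do carry working limits, such as CK above 10 x ULN or conjugated bilirubin above 1.5 x ULN.
6. **Entry rule.** Known statin allergy or intolerance excludes a patient (4.2.8). That lowers the risk, but it is not an on-treatment rule.

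**Size.** The documents give no incidence of allergic reactions, so every rate below is an assumption, shown as a range:
- any suspected allergic reaction over 24 months: 0.1% to 2%;
- share of those with airway, respiratory or circulatory signs: 10% to 50%;
- share of those graded mild and self-limited, so that the restart default applies: 25% to 75%.

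The per-subject risk is the product of the three:
- low: 0.001 x 0.10 x 0.25 = 0.000025;
- high: 0.02 x 0.50 x 0.75 = 0.0075.

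For the active arm, n = 40 (Section 9.3.1):
- expected subjects: 40 x 0.000025 = 0.001 to 40 x 0.0075 = 0.3;
- chance of at least one: 1 - (1 - 0.000025)^40 = 0.1% to 1 - (1 - 0.0075)^40 = 26.0%.

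As a ceiling, if every such reaction were graded mild, the high per-subject risk is 0.02 x 0.50 = 0.01. That gives 40 x 0.01 = 0.4 subjects and 1 - 0.99^40 = 33.1%. The ceiling includes reactions that already stop drug.

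**The case against.** The strongest reply is that a stop is already part of the pathway. The Synopsis says dose reduction is allowed, Section 3.4 also says the dose may be reduced according to tolerance, and Section 9.1 lists discontinuation among the instructions the trial nurse can give. Section 7 requires a continue-or-stop assessment of each reported event, and Section 8 requires a stop when withdrawal is judged best for the subject. Events possibly related to the statin are reviewed like SAEs (10.4.1.3), alarming or serious events reach the PI and the independent monitor within 24 hours (10.4.4), and that monitor can advise on management (10.3.2). All of this stands and makes an actual re-exposure less likely. But it is general discretion. The examples attached to the best-interest criterion are drug interaction and glycemic control, and none of these passages alters the mandatory wording in 7.2.

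Second, the words mild and self-limited qualify every sign in the cell, and physicians know what anaphylaxis is. That is fair, but the row still gives no criterion for these three signs, while the grade decides dosing.

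Third, thresholds may exist in material that is not reproduced: the management algorithms (7.1), the adapted CTCAE dictionary and operating manual (10.3.2), and the coding guide (10.4.1.2). This cannot be checked, so the finding is limited to the protocol text.

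Fourth, the size is small and wholly assumed, the upper figure needs all three upper bounds together, and no credit is given for the safeguards. That is correct, and the figures should be read as an outer range.

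Fifth, moving signs to Category C could stop drug after a reaction with another cause, such as gadolinium at one of the three MRIs. This is largely answered: Table 2 is captioned as statin-related events, Section 7 limits managed events to those at least possibly related to the study intervention, and the existing anaphylaxis entry works in the same way.

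**Conclusion.** The concern holds as a matter of protocol text. Followed literally, the default re-exposes a subject to the suspected drug after airway edema, bronchospasm or hypotension judged mild, and nothing written fixes where mild ends. It is not a missing stop rule: anaphylaxis, the two severe skin reactions and severe allergic reactions do stop drug, and discretion can prevent a restart in the rest.

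The expected number affected is small, 0.001 to 0.3 active-arm subjects under rates that are all assumed. The change is worth making because the potential harm is serious and a wording amendment removes the default that leads to it. Confidence is high for the text. Whether staff materials already close the gap in practice is unknown.

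**What to change.** 1. In the allergic-reactions row of Table 2, move airway edema, bronchospasm and hypotension from Category B to Category C. Category B keeps mild self-limited pruritus, hives or urticaria, flushing, peripheral edema and tachycardia.
2. Add to 7.2: *The Category B restart does not apply after a suspected study-drug hypersensitivity reaction with airway, respiratory or circulatory signs (airway edema, bronchospasm or hypotension), rated possibly, probably or definitely related under 10.4.2.1. Study drug is stopped under Section 8 and follow-up continues to 24 months.*
3. Add *except as stated in 7.2* to the Category B sentences in 3.4 and 5.1.

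This is a wording amendment with no added visits or data. The downside is a very few extra discontinuations, each with the unblinding that 7.2 attaches to Section 8 events. They can fall in either arm because the rule is applied blind. If the placebo rate lies between zero and the active-arm rate, the extra stops across 80 subjects run from 0.001 (low active-arm rate, no placebo cases) to 80 x 0.0075 = 0.6, with a ceiling of 80 x 0.01 = 0.8. Outcome follow-up is kept, because Section 8 follows subjects who reach a safety endpoint through the 24-month visit.
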